### **Protocol**

Study Period: January 1, 2017, to December 31, 2023, retrospective study. Study Location: Seven tertiary Grade A hospitals in China: The First Affiliated Hospital of Zhejiang University School of Medicine, Zhejiang Cancer Hospital, Taizhou Hospital of Zhejiang Province, West China Hospital of Sichuan University, The Third Affiliated Hospital of Sun Yat-sen University, The First Affiliated Hospital of China Medical University, and The First

Affiliated Hospital of Xinxiang Medical University. Inclusion Criteria: All patients who underwent biopsy for focal pancreatic lesions, including US-guided FNA or CNB, EUS-guided FNA or FNB, to obtain cytological or histological specimens of the pancreas for pathological examination. Exclusion criteria: ① Patients with incomplete or missing case data (imaging, laboratory tests, pathological examinations); ② Patients with less than 12 months of clinical follow-up, lost to follow-up, or incomplete follow-up data; ③ Patients who underwent intraoperative biopsy; ④ Patients who underwent fluid aspiration procedures.

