
lyophilized powder and is reconstituted with 2 ml of a specific solution to form a homogeneous microbubble suspension. A 0.5 ml bolus of this suspension is administered, followed by a 5 ml saline flush. The arterial phase enhancement process begins immediately after aortic enhancement, lasting for 10 to 30 seconds, followed by the venous phase, which persists for 30 to 120 seconds. Routine archiving of imaging data is performed.

The baseline data of enrolled patients were collected from the electronic medical record system, including the patients' names, genders, hospital admission numbers, examination numbers, puncture dates, and body mass index (BMI). Collect all imaging data (CT, MR, ultrasound, PET, and MRCP, etc.) of the patient on the integrated imaging system, and evaluate and record the imaging characteristics of focal pancreatic lesions. The indicators include the location of the lesion, which is divided into the head, uncinate process, neck, body, and tail; the size of the lesion, measured by the puncture operator and assistant on the maximum cross-section of the lesion displayed on the ultrasound image, with the average value recorded; and the exophytic retrograde morphology of the lesion, assessed by CT or MR. This term refers to the lesion morphology originating from the innermost edge of the pancreas and extending posteriorly beyond the pancreas, or presenting as a perivascular soft tissue sheath surrounding the superior mesenteric artery or celiac trunk, rather than a distinct mass. This is an atypical feature of common pancreatic lesions and is therefore easily overlooked. Information related to pancreatic puncture, including previous puncture history, imaging guidance method, puncture technique, needle gauge, puncture path, auxiliary techniques (contrast-enhanced ultrasound or coaxial technique), operator, post-puncture pathological results, complication status, and repeat puncture status, is collected and recorded by an assistant through the electronic medical record system.

After the puncture, follow-up education is provided to the patient, including a 12-month clinical follow-up. The follow-up encompasses surgical pathology results, repeat puncture pathology results, imaging examination results (CT, MRI, and ultrasound), laboratory test results (complete blood count, liver and kidney function, blood biochemistry, tumor markers, blood and urine amylase), and case records (outpatient and inpatient records).

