12 months of clinical follow-up (including medical history, laboratory tests, imaging studies, and pathological examinations). When post-puncture histopathological diagnosis indicates inflammation or an inconclusive result, further confirmation of the disease nature is required. If the biopsy results suggest inflammation or are inconclusive, but clinical and imaging evidence strongly indicate malignancy, a repeat biopsy or sampling is recommended. The necessity for repeated sample collection is determined through multidisciplinary discussion. For patients without indications for repeat biopsy, at least 12 months of clinical dynamic monitoring is required, including medical history, imaging (CT or MR), and tumor marker tests. Cases where the lesion size remains stable (diameter increase  $\leq 20\%$ ), exhibit imaging characteristics of benign lesions, and show no change in tumor markers are classified as benign. Cases with a diameter increase  $> 20\%$  and an absolute increase of more than 5 mm, along with an increase in tumor markers, are classified as malignant. Based on clinical follow-up of at least 6 months post-procedure, cases ultimately diagnosed as benign were considered true negative results, while those ultimately diagnosed as malignant were considered false negative results. The probability of diagnostic inaccuracy was the percentage of the sum of false positive and false negative cases out of the total number of cases. The secondary study endpoints were the incidence rates of severe complications, mild complications, and repeat biopsy after EUS and US-guided pancreatic biopsy. Post-procedure complications were assessed and graded according to the clinical practice guidelines of the Society of Interventional Radiology. Adverse events related to puncture occurring within 30 days post-operation fall under the category of complications. These include immediate post-puncture bleeding or hematoma, vagal reflex, infection, puncture-related pancreatitis, organ rupture (duodenum or colon), arteriovenous fistula, and arterial dissection.

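### The primary endpoint pools tissue verification with a stricter surveillance rule; if the mix differs by route, part of the difference in inaccuracy may be verification, not biopsy error

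*Protocol*

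**What the plan says.** All of this stands in the protocol's section headed Protocol. The primary endpoint is false positives plus false negatives, divided by all cases. A biopsy read as inflammation or as inconclusive (index-negative below) counts as a true negative if the final diagnosis is benign and as a false negative if it is malignant.

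That final diagnosis can rest on different evidence: "The follow-up encompasses surgical pathology results, repeat puncture pathology results, imaging examination results (CT, MRI, and ultrasound"), together with laboratory tests and case records.

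- **Tissue.** Where an index biopsy is negative, "but clinical and imaging evidence strongly indicate malignancy, a repeat biopsy or sampling is recommended". On who makes that decision, the protocol says only this: "The necessity for repeated sample collection is determined through multidisciplinary discussion". Some patients also have surgical pathology.
- **Surveillance.** "For patients without indications for repeat biopsy, at least 12 months of clinical dynamic monitoring is required". A benign call needs stable size, benign imaging features and unchanged markers. A malignant call needs a diameter increase above 20% "and an absolute increase of more than 5 mm, along with an increase in tumor markers, are classified as malignant".

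Repeat biopsy is also an outcome. The secondary endpoints are the "incidence rates of severe complications, mild complications, and repeat biopsy after EUS and US-guided pancreatic biopsy". The data are historical: "Study Period: January 1, 2017, to December 31, 2023, retrospective study". Confounding is handled by 1:1 nearest-neighbor propensity score matching with a caliper of 0.02. The protocol describes neither a final diagnosis made blind to route nor a breakdown by the standard that settled it.

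**The concern.** The two standards differ in strength. Surgical or repeat pathology can reveal a missed cancer directly. The surveillance rule needs three things at once, so it may leave some missed cancers unlabeled. Which standard a patient receives is a clinical decision made after the index biopsy, with its route and result known.

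If one route has more of its index-negative cases settled by tissue, more of its misses are found and counted. The other route keeps more of its misses among the apparent true negatives. The primary comparison would then mix biopsy error with intensity of verification. Matching balances variables between groups; it cannot equalize what happens after the biopsy.

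The protocol gives some reason to ask whether verification differs. EUS biopsy is done under intravenous general anesthesia and US biopsy under local lidocaine, so the burden of repeating may differ. The Background says percutaneous techniques can obtain more histological specimens, so inconclusive results may not be equally common. These are reasons to look, not evidence of a difference.

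**Working it through.** **Inputs from the protocol.** The endpoint formula, the two ways of reaching a final diagnosis, and the three-part malignant rule. The protocol states no miss rate, verification share, detection rate of surveillance or sample size, so there is no planned figure to reproduce. Every number below is an assumption.

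**Model.** Let *f* be the true share of biopsies that are missed cancers, equal in both arms. Let *v* be the share of those misses settled by tissue, taken as error-free. Let *s* be the share of the remaining misses that surveillance ends up calling malignant. False positives are set aside.

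Observed inaccuracy = f × [v + (1 − v) × s]

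Gap between arms = f × (1 − s) × (v₁ − v₂)

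**Results at f = 8%.**

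| s | v₁ / v₂ | Arm 1 | Arm 2 | Gap (points) |
|---|---|---|---|---|
| 0.5 | 0.7 / 0.4 | 8% × 0.85 = 6.8% | 8% × 0.70 = 5.6% | 1.2 |
| 0.5 | 0.8 / 0.4 | 8% × 0.90 = 7.2% | 8% × 0.70 = 5.6% | 1.6 |
| 0.9 | 0.7 / 0.4 | 8% × 0.97 = 7.76% | 8% × 0.94 = 7.52% | 0.24 |
| 0.9 | 0.8 / 0.4 | 8% × 0.98 = 7.84% | 8% × 0.94 = 7.52% | 0.32 |
| 1, any v; or any s with v₁ = v₂ | | | | 0 |

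**Wider range.** With f from 5% to 15%, s from 0.5 to 0.9, and v of 50% against 70% or 40% against 80%, the gap runs from 0.1 to 3.0 points. At f = 10%, s = 0.5 and v of 40% against 80%, observed inaccuracy is 7.0% against 9.0%. A two-proportion test at two-sided 0.05 (two-sidedness assumed) then finds significance against the more-verified arm with probability 14.5%, 21.3% and 37.8% at 300, 500 and 1000 per arm. The nominal figure in that direction is 2.5%. The order can also reverse: true rates of 12% (v = 40%) and 10% (v = 80%) appear as 8.4% and 9.0% at s = 0.5. At s = 0.7 they appear as 9.84% and 9.4%, with no reversal.

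**How candidate sensitivity analyses behave.** Take 500 per arm, 100 index-negatives, 40 true misses (8%), 80% of tissue-verified index-negatives malignant, v = 0.7 and 0.4, s = 0.5.

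- Arm 1: 28 misses found by tissue among 28 / 0.8 = 35 verified cases. Of 65 under surveillance, 12 are misses, 6 are detected, and 59 are labeled benign.
- Arm 2: 16 misses found among 16 / 0.8 = 20 verified cases. Of 80 under surveillance, 24 are misses, 12 are detected, and 68 are labeled benign.
- Planned count: 34/500 = 6.8% against 28/500 = 5.6%.
- All surveillance-only benign cases counted as false negative: (34 + 59)/500 = 18.6% against (28 + 68)/500 = 19.2%.
- Malignant fraction of verified cases (80%) applied: (34 + 47.2)/500 = 16.2% against (28 + 54.4)/500 = 16.5%.
- Same fraction *p* in both arms: the arms meet when 34 + 59p = 28 + 68p, so p = 6/9 = 67%.
- Different fractions: the hidden misses are 6/59 = 10.2% and 12/68 = 17.6%. Reclassifying these gives 40/500 = 8% in both arms.

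The two extreme reclassifications more than double the true 8% and reverse the order. A common fraction closes the gap only at 67%, while modest unequal fractions close it exactly. The fractions must therefore be allowed to differ between arms.

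**The case against.** **One pathway for both routes.** The protocol states a suspicion trigger for repeat sampling, a multidisciplinary decision, written surveillance criteria and exclusion of anyone with under 12 months of follow-up, the same for EUS and US. This stands, and it would be too strong to say that verification was left to chance. It limits the problem without removing it, because the type of standard stays discretionary and is not said to be blind to route. The same section also bases true- and false-negative status on at least 6 months, which must be reconciled with the 12-month requirement.

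**The repeat-biopsy endpoint proves nothing about verification.** A reader might infer that, by comparing repeat-biopsy rates, the plan concedes unequal verification, and that the route with more repeats is the one made to look worse. The protocol does not support this. Repeats are recommended when a miss is suspected, so a higher rate may reflect more true misses. The rate alone cannot show which arm is biased, or whether either is.

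**Surveillance may miss little.** A benign call also has three conditions, so a growing lesion without a marker rise fits neither class and is not automatically a true negative. Case records and later surgery can also establish malignancy. This stands: *s* may be close to 1, where the gap is small.

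**Mixed standards are usual, and analysis detail may sit in an SAP.** A composite reference is normal in a retrospective biopsy study, and restricting to pathology would bring its own selection. An SAP that is not shown may hold a tabulation or sensitivity analyses. The point therefore rests on the endpoint definition that the protocol itself fixes, not on the absence of such analyses.

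**Conclusion.** The concern holds in conditional form. As defined, the primary endpoint lets verification enter the route comparison, and matching cannot take it out. Bias arises only if two things are both true: the share of index-negative cases settled by tissue differs by route, and surveillance misses some cancers. The protocol reports neither quantity. Size and direction are therefore unknown. At an assumed true miss rate of 8%, the illustrative range is 0.2 to 1.6 points, and zero if either condition fails. The documents do not show that one route is in fact verified more, or that the planned result will be wrong. They show that the planned count alone cannot tell a route difference from a verification difference.

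**What to change.** 1. For each index-negative case, code which standard settled it: surgery, repeat biopsy or surveillance only. Tabulate this by arm.
2. Beside the planned matched comparison, report a tipping-point analysis that reclassifies a range of fractions of surveillance-only benign cases as false negative. Use the same range in both arms, and also let the fractions differ between arms.
3. Show two outer bounds: all such cases counted as false negative, and the malignant fraction seen in verified cases. Neither should veto a conclusion. The first labels genuine inflammatory lesions as errors. The second carries over a fraction from cases selected because malignancy was suspected.
4. State the fractions at which the route difference loses significance or changes direction, and qualify the conclusion if they are plausible.

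The protocol already collects surgical pathology, repeat-puncture pathology and repeat-puncture status, and patient care is unaffected. The cost is one coded field, two or three extra analyses and a possibly less sharp conclusion. If verification proves similar by route, the primary comparison is strengthened.

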All EUS-FNA/FNB procedures were performed using a linear array echoendoscope (GF-UCT240, Olympus Medical Systems, Tokyo, Japan) and an ultrasound biopsy needle (Echotip, Cook Medical, Bloomington, USA). The biopsy needles included 25G, 22G, and 19G models, with the 22G FNA or FNB needle being the most widely used in our study. Under intravenous general anesthesia, the tip of the echoendoscope was inserted through the oropharynx into the gastric fundus, pylorus, and duodenum. After locating the target pancreatic lesion, the tip of the echoendoscope was fixed. For transgastric wall puncture, 25G, 22G, and 19G needles can be selected based on the type of lesion, surrounding tissue structure, and the operator's experience. When performing transduodenal wall puncture, considering the flexibility of the needle, 22G or 25G needles are chosen. Under endoscopic ultrasound guidance, if the FNA technique is used, the needle is inserted into the target lesion, and tissue or cells are obtained using the "slow pull" technique and negative pressure aspiration. The aspirated cell clusters are smeared and fixed with 95% alcohol for smear cytology examination; or placed in a liquid-based cell vial for liquid-based cytology examination. Simultaneously, the aspirated tissue is fixed in 10% formalin solution and sent for histopathological examination. When employing the FNB technique, the biopsy needle is inserted into the target lesion, and the lesion is excised using a specially shaped needle tip to collect tissue into the hollow core of the needle. After withdrawing the biopsy needle, the tissue is fixed in a 10% formalin solution. In this study, all cases utilized the Macroscopic On-Site Quality Evaluation (MOSE) technique, where the operator conducts an initial visual assessment of the extracted specimen. If the amount of tissue or cells obtained is insufficient for pathological evaluation, the biopsy procedure can be repeated until the specimen meets the pathological requirements. Preoperative and intraoperative use of Sonazoid (16ul/2ml, GE, USA) for contrast-enhanced ultrasound aids in assessing the blood supply within and around the target lesion. Sonazoid contrast agent is provided in lyophilized powder form and reconstituted with 2 ml of a specific solution to form a uniform microbubble suspension. A 2 ml bolus of this suspension is administered, followed by a 5 ml saline flush. The arterial phase enhancement process begins immediately after aortic enhancement, lasting 10 to 30

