
seconds, followed by the venous phase, which lasts 30 to 120 seconds. Routine archiving of imaging data is performed.

The ultrasound systems (Mindray, Shenzhen, China; Aloka, Tokyo, Japan; Esaote, MyLab 9, Florence, Italy) were equipped with ultrasound transducers (3.5 MHz convex array probes) for guiding and monitoring percutaneous pancreatic biopsy. The procedure was performed using CNB or FNA techniques. If the CNB technique was employed for tissue sampling, an automated core biopsy needle (18G and 16G, Magnum Bard, Covington, GA, USA) was used directly or guided by a coaxial needle; in FNA, a negative pressure aspiration biopsy needle (18G and 21G, HAKKO medical, Japan) was utilized. After preparing the skin, disinfecting, and draping at the puncture site, 1% lidocaine is used for layer-by-layer infiltration anesthesia at the intended puncture area. Under ultrasound guidance, an 18G fully automatic core biopsy needle is advanced to the anterior edge of the target pancreatic lesion, with the path options including direct, transgastric, or transhepatic routes. After activating the biopsy device, the specimen is retrieved and placed on filter paper, then promptly fixed in 10% formalin solution for histopathological examination. Typically, a single biopsy specimen measures 19mm in length and 1mm in width. If the sample is insufficient or the tissue appearance is inconsistent with pancreatic tumor, additional puncture biopsies can be immediately performed. If the FNA technique is used for sampling, an 18G or 21G puncture needle is inserted into the target pancreatic lesion. First, create negative pressure by pulling the device, then move the puncture needle up and down multiple times to obtain the specimen. The obtained cell clusters are smeared, then fixed in 95% alcohol for smear cytology examination. Meanwhile, the aspirated tissue strips are fixed in 10% formalin solution for histopathological examination. The operator conducts a preliminary macroscopic assessment of the retrieved specimens. If the specimen quantity is insufficient or its appearance does not match the disease, additional puncture biopsies can be performed until the specimen quantity meets the pathological requirements as assessed macroscopically. After puncture, routine examination of the puncture site and needle tract is necessary to early identify puncture-related complications. If signs of bleeding in the needle tract are observed, gelatin sponge can be inserted through the coaxial needle, or immediate compression hemostasis can be performed. Preoperative and intraoperative use of SonoVue (59 mg/vial, Bracco, Milan, Italy) or Sonazoid (16ul/2ml, GE, USA) for contrast-enhanced ultrasound (CEUS) aids in evaluating the blood supply within and around the target lesion. SonoVue contrast agent is provided in lyophilized powder form and reconstituted with 5 ml saline to form a uniform microbubble suspension. In use, 2.4 ml of this suspension is injected as a bolus, followed by a 5 ml saline flush. Sonazoid contrast agent is provided in the form of

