The primary endpoint of this study was the inaccuracy of EUS- and US-guided pancreatic biopsy in diagnosing focal pancreatic lesions. Cases were classified as true positive results if the histopathological diagnosis post-biopsy was pancreatic ductal adenocarcinoma (PDAC), pancreatic neuroendocrine tumor (PNET), or other definitive malignant or benign pancreatic tumors, and if these findings were consistent with the results of at least

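### The primary endpoint is scored on histopathology only, although cytology is eligible and FNA in both arms produces it, so a cancer diagnosed on cytology can be counted as a false negative

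*Protocol*

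**What the plan says.** All places are in the Protocol section of the protocol.

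- **Eligibility.** Patients qualify if sampled by any of four techniques, "including US-guided FNA or CNB, EUS-guided FNA or FNB", "to obtain cytological or histological specimens of the pancreas for pathological examination". FNA is therefore allowed in both arms, and cytology is an accepted specimen type.
- **EUS procedure.** FNA cell clusters are smeared or "placed in a liquid-based cell vial for liquid-based cytology examination". The same session also yields tissue: "Simultaneously, the aspirated tissue is fixed in 10% formalin solution and sent for histopathological examination".
- **US procedure.** FNA is handled in parallel: "The obtained cell clusters are smeared, then fixed in 95% alcohol for smear cytology examination", while tissue strips go to histology. For FNB and CNB the protocol describes only formalin-fixed tissue.
- **True-positive rule.** "Cases were classified as true positive results if the histopathological diagnosis post-biopsy was pancreatic ductal adenocarcinoma (PDAC"; the sentence then adds neuroendocrine and other definite tumours and requires consistency with a minimum of 12 months' follow-up.
- **Inconclusive branch.** "When post-puncture histopathological diagnosis indicates inflammation or an inconclusive result", the nature of the disease must be confirmed. A case finally benign is then a true negative, and a case finally malignant is a false negative.
- **Endpoint.** False positives plus false negatives, divided by all cases.

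No sentence says how a cytology result enters this classification.

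**The concern.** The procedure paragraphs treat cytology and histopathological examination as two separate tests on material from one session. The two sentences that sort cases then name only the second. If they are followed literally, a session that established a cancer on the smear can be scored as a diagnostic failure because the tissue fragment was inconclusive. The error lies in the index-test result; follow-up supplies only the reference standard.

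Only FNA has a described cytology result to lose, so the rule treats FNA differently from FNB and CNB. The analysis compares pooled EUS-FNA/FNB with pooled US-FNA/CNB, and the stated subgroups are lesion size, location and morphology. No described analysis separates FNA from the other techniques, so the problem would not show itself. If centres read the term differently, the endpoint may also be scored differently across the seven hospitals.

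**Working it through.** The protocol gives no event rate, FNA share or cytology-histology discordance rate, so there is no planned figure to reproduce. The check has two steps.

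**Step 1: trace the case types through the rule.**

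| Cytology | Histology | Final diagnosis | Class as written | Class on combined report |
|---|---|---|---|---|
| Diagnostic of cancer | Diagnostic of cancer | Malignant | True positive | True positive |
| Diagnostic of cancer | Inconclusive or inflammatory | Malignant | **False negative** | True positive |
| Diagnostic of cancer | Inconclusive or inflammatory | Benign | True negative | False positive |
| Diagnostic of cancer | None | Malignant | **No class** | True positive |
| Not diagnostic | Inconclusive or inflammatory | Malignant | False negative | False negative |

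The second row is the mis-scoring. The third row is the price of the combined rule. The fourth row matters only if cytology-only cases exist. They are eligible by the inclusion wording, but both FNA descriptions also send tissue to histology. Such a case could also be argued out under the exclusion for incomplete pathology data.

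**Step 2: effect on the endpoint.** Let f be the share of FNA in an arm. Let d be the probability, among FNA cases, of diagnostic cytology with inconclusive or inflammatory histology in a finally malignant lesion (the second row). Then

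- added inaccuracy in an arm = f × d
- shift in the EUS − US difference = (f_EUS − f_US) × d, taking d as equal in both arms.

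Both f and d are assumptions, shown over a range because the documents give neither:

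| f_EUS / f_US | d | Added, EUS | Added, US | Net shift (EUS − US) |
|---|---|---|---|---|
| 50% / 50% | 2% to 10% | 1.0 to 5.0 points | 1.0 to 5.0 points | 0 |
| 70% / 30% | 2% to 10% | 1.4 to 7.0 | 0.6 to 3.0 | +0.8 to +4.0 |
| 90% / 10% | 2% to 10% | 1.8 to 9.0 | 0.2 to 1.0 | +1.6 to +8.0 |
| 30% / 70% | 2% to 10% | 0.6 to 3.0 | 1.4 to 7.0 | −0.8 to −4.0 |

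For example, at 70% / 30% and d = 5%: 0.70 × 5 = 3.5 points in EUS, 0.30 × 5 = 1.5 in US, net 2.0. If d differs by arm, the shift is f_EUS × d_EUS − f_US × d_US, and the documents do not fix that either.

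**The case against.** The best defence is that histopathological is used loosely for the whole pathology report. The wording is not uniform. Data collection records pathological results in general, and the sentence recommending repeat sampling speaks of biopsy results. This stands to the extent that nobody can say from the protocol that cases were in fact scored on histology alone. It does not remove the point. The first term is a data item and the second belongs to a recommendation on resampling, whereas both sentences that sort cases use the narrower term, which the procedure paragraphs set against cytology. If the usage is loose, the endpoint is ambiguous and needs the same clarification.

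Three further objections hold. A finally benign case in the inconclusive branch is a true negative, so the error is confined to finally malignant lesions. Scoring either test as positive can create false positives. Finer categories, such as suspicious or atypical cytology, may reasonably be left to a SAP.

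A reader might infer that the error falls mainly on EUS, as the FNA arm. The documents do not support that. Both arms include FNA with cytology, and no FNA share is given for either. The remark that 22G was the commonest EUS needle concerns gauge and groups FNA with FNB. Any figure for bias against EUS would have to assume the imbalance it claims to show.

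**Conclusion.** The point holds as a defect in the definition of the primary endpoint. Followed as written, the rule counts a finally malignant lesion with diagnostic cytology and inconclusive or inflammatory histology as a false negative, and it leaves any cytology-only case without a class.

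Inaccuracy can be overstated for FNA cases in either arm, by f × d. With a common discordance rate, the EUS-US comparison is biased only if the FNA shares differ. The shift is then against whichever arm uses more FNA: 0.8 to 4.0 points for an assumed 70/30 split with d of 2% to 10%, and zero at equal shares. These figures are illustrations on assumed inputs. The documents establish neither the size nor the direction of a difference between arms. The change should be made, but the text does not show that the comparison is in fact distorted.

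**What to change.** - Define the index result, identically in both arms, as the combined cytology and histology report of the index session: positive if either is diagnostic of a tumour, inconclusive only if neither is.
- State that a positive result contradicted by follow-up is a false positive. The endpoint formula counts false positives, but the protocol only implies their definition.
- Report the FNA share by arm, before and after matching, so that readers can judge whether the rule could affect the comparison.
- Report a sensitivity analysis that scores histology only.

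**Cost.** A change of endpoint wording and one extra analysis. Puncture technique is already collected, so the FNA share needs no new data. The combined rule may add some false positives, which the sensitivity analysis will help to show. The data-collection list names only pathological results, so where cytology was not recorded separately some reports at the seven hospitals will have to be re-read.
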